### 6.16.1.2. Symptom Resolution

Participants will be assessed for the presence of symptoms associated with COVID-19 by a daily questionnaire. This questionnaire is for outpatient participants only.

The questionnaire contains these symptoms:

shortness of breath or difficulty breathing congestion or runny nose fever chills sore throat stomachache nausea vomiting diarrhea cough tiredness muscle or body aches and pains headache loss of taste loss of smell poor appetite or poor feeding

The presence or absence of symptoms associated with COVID-19 within the past 24 hours will be collected from participants or their parents/legal guardian.

Symptom resolution is defined as all symptoms on the symptom questionnaire scored as absent.

The proportion of participants that achieve symptom resolution at Days 5, 7, 11, and 22 will be summarized in frequency tables and listed.

# 6.16.1.3. Time to Symptom Resolution and Sustained Symptom Resolution Time to symptom resolution is defined (in days) as:

(First study day when symptom resolution status is changed to "Yes" - Infusion Date + 1)

If a patient has not experienced symptom resolution by completion or early discontinuation of study/study treatment, the patient will be censored at the date of their last visit during the treatment period. If a patient is hospitalized, the patient will be censored at the date of hospitalization.

Time to symptom resolution will be evaluated during the study treatment period only and will be summarized and listed.

Time to symptom resolution will be presented graphically.

Sustained symptom resolution occurs at the first visit where symptom resolution is observed without reoccurrence at any subsequent visits. Time to sustained symptom resolution in the same manner as described for initial symptom resolution and will be analyzed and summarized in the same way.

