2.7.2. Section 5.2. Exclusion Criteria

Participants are excluded from this addendum if any of the following criteria apply:

9. SpO₂ ≤ 93% on room air at sea level, or while on chronic oxygen therapy and/or respiratory support due to underlying non-COVID-19 related comorbidity, respiratory rate ≥30 per minute, and heart rate ≥125 per minute due to COVID-19 (FDA February 2021)
10. Require mechanical ventilation or anticipated impending need for mechanical ventilation due to COVID-19
11. Have known allergies to any of the components used in the formulation of the interventions
12. Have hemodynamic instability requiring use of pressors within 24 hours of randomization
13. Suspected or proven serious, active bacterial, fungal, viral, or other infection (besides COVID-19) that in the opinion of the investigator could constitute a risk when taking intervention
14. Have any co-morbidity requiring surgery within 7 days, or that is considered life-threatening within 29 days
15. Have any serious concomitant systemic disease, condition or disorder that, in the opinion of the investigator, should preclude participation in this study.
16. This criterion is not applicable for participants in this addendum
17. This criterion is not applicable for participants in this addendum
18. This criterion is not applicable for participants in this addendum
19. Have received treatment with a SARS-CoV-2 specific monoclonal antibody or remdesivir within 90 days before dosing
20. Have received convalescent COVID-19 plasma treatment within 90 days before dosing
21. This criterion is not applicable for participants in this addendum
22. Have participated, within the last 30 days, in a clinical study involving an investigational intervention. If the previous investigational intervention has a long half-life, 5 half-lives or 30 days, whichever is longer, should have passed.
23. Are concurrently enrolled in any other type of medical research judged not to be scientifically or medically compatible with this study
24. Are currently pregnant or breast feeding
25. Are investigator site personnel directly affiliated with this study
29. This criterion is not applicable for participants in this addendum

31. Have a diagnosis of MIS-C in the opinion of the investigator
32. Are currently hospitalized for treatment of COVID-19. Other reasons for hospitalization are acceptable.

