Estimates of continuous efficacy, safety, and health outcome variables with a single postbaseline timepoint will be made using analysis of covariance (ANCOVA) with baseline value in the model. The LS mean, standard error, and 95% CI, unless otherwise specified, will also be reported. Missing data imputation method for the ANCOVA model is specified in Section 6.3.

Estimates of binary endpoints will be made using logistic regression. The model will include the weight range groups used for dosing, unless otherwise noted. The CIs of any rate estimates will be reported.

The Kaplan-Meier (KM) product limit method will be used for time-to-event analyses. Time for all analyses will be described in units of days.

For all change from baseline analyses, patients who do not have a valid baseline measure will be excluded.

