# 6.10. Efficacy Analyses

The analysis of the viral load lab results will utilize the following conventions:

For qualitative endpoints in the trial (viral clearance yes/no, time to viral clearance) the lab determination of "positive"/ "negative" will be used. SARS-CoV-2 clearance (yes/no) is defined as 2 consecutive negative tests for the SARS-CoV-2 virus. The date of viral clearance is defined as the earliest date of the 2 consecutive negative tests.

For quantitative endpoints in the trial (change from baseline, area under the response viral load curve [AUC]), the viral load will be derived based on cycle threshold (Ct) values with the following considerations:

Two Ct values will be provided on 2 different genes: N1 and N2. N1 will be used as the primary measure; N2 will only be used when the Ct value for N1 is not available.
Ct values range between 0 and 45.
Negative CoV-2 tests will be associated with a Ct value of 45.
The (log base 10) viral load will be calculated from the Ct value (45-Ct)/log 10, or (45-Ct)/3.321928.

□ A normalization step will also be applied. The viral load Ct value described in the previous steps will be subtracted by (RP Ct – 26.17), where RP Ct is a measure for the amount of material in the sample and 26.17 is a historical average value of RP Ct for this assay, used here to center the RP Ct values.

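### Sustained symptom resolution can rest on one clear record at the last symptom visit, and any hospitalization is censored as if unrelated to recovery

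*SAP*

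**What the plan says.** **Definition.** SAP 6.16.1.3: "Sustained symptom resolution occurs at the first visit where symptom resolution is observed without reoccurrence at any subsequent visits". No minimum symptom-free duration, number of visits or confirming visit is given. The sustained endpoint "will be analyzed and summarized in the same way" as simple resolution, so the same censoring rules apply to both.

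**Censoring.** For a child not resolved by completion or early discontinuation, "the patient will be censored at the date of their last visit during the treatment period". For admissions, "If a patient is hospitalized, the patient will be censored at the date of hospitalization", with no limit by cause or timing. SAP 6.1.4 adds: "The Kaplan-Meier (KM) product limit method will be used for time-to-event analyses". No competing-event method is named for this endpoint.

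**Collection.** SAP 6.16.1.2 says symptoms are assessed "by a daily questionnaire", for outpatients only. In the Protocol Schedule of Activities (2.2.1) the symptom row has 11 marks: screening, Day 1, Days 2 to 4, 5, 6, 7, Days 8 to 10, 11, 22, 29 and early discontinuation (ED). There is none for Days 12 to 21, 23 to 28, 60 or 85.

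**Missing data.** SAP 6.3.6 carries the last post-baseline symptom record forward (mLOCF). It sets time points after death to the category Severe, although the items are recorded only as present or absent.

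**Related text.** SAP 6.10 requires confirmation for viral clearance: "SARS-CoV-2 clearance (yes/no) is defined as 2 consecutive negative tests for the SARS-CoV-2 virus". Protocol exclusion 32 bars children in hospital for COVID-19 but adds "Other reasons for hospitalization are acceptable".

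**The concern.** A sustained endpoint should differ from a simple one because recurrence had a chance to show. At the last symptom assessment there is no later visit, so the no-recurrence condition is met by default and the two endpoints coincide. The same happens when a child discontinues on a clear visit, except that the event then falls early on the curve. The mLOCF rule does not help, because it carries the clear record forward as clear.

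The hospitalization rule is a separate matter. Kaplan-Meier treats a censored child as having the same future recovery as those still followed. Admission for COVID-19 during unresolved illness is unlikely to satisfy that.

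At stake is how the sustained curve is read, mainly its Day 29 value. The primary PK endpoint and the safety analyses are not affected.

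**Working it through.** The documents give no resolution rate, relapse rate, dropout rate or event count for this endpoint, so there is no planned figure to reproduce.

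**1. Last-visit rule, closed form.** Assume exponential recovery from Day 1 with a median of 7 or 12 days, no dropout and no admissions. With a confirmation rule no event can be dated Day 29, so the Day 29 estimate stays at its Day 22 value.

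| Median (assumed) | Resolved by Day 22 | Resolved by Day 29 | Gap |
|---|---|---|---|
| 7 days | 1 − 2^(−21/7) = 87.5% | 1 − 2^(−28/7) = 93.75% | 6.25 points |
| 12 days | 1 − 2^(−21/12) = 70.3% | 1 − 2^(−28/12) = 80.2% | 9.9 points |

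All of this gap is real resolution that cannot be confirmed. Now let a child who is still ill have probability q of a transient clear record at a visit. False sustained events by Day 29 then equal q × (share still unresolved at Day 29). With q of 5% or 15% (assumed):

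- median 7: 0.05 × 6.25% = 0.3 points, to 0.15 × 6.25% = 0.9 points
- median 12: 0.05 × 19.8% = 1.0 point, to 0.15 × 19.8% = 3.0 points

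**2. Last-visit rule, simulation.** 20,000 simulated children per scenario on the actual visit grid (Days 1 to 11, 22, 29), with the same medians and q, admission 1.5% or 5%, dropout 0% or 10%, and admitted children not resolved by Day 29 (all assumed):

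- Share of sustained events resting on one final record: 6.7% to 15.1%.
- Fall in the Day 29 estimate under two-visit confirmation: 6.3 to 12.0 points. With q = 5%, 1.5% admitted and no dropout it goes from 94.0% to 87.7% (median 7) and from 80.8% to 70.4% (median 12).
- Change at Days 5 to 22: at most 0.5 points without dropout and 1.4 points with 10% dropout.

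**3. Hospitalization rule.** If k of n children are admitted before resolving and before others resolve, Kaplan-Meier with censoring gives F(t), and keeping them unresolved gives F(t) × (n − k)/n. The censored curve can never be the lower one.

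- Protocol 2.5 (Section 4.2) gives 0.1% to 1.5% of infected children hospitalized. SAP 5.3 gives about 50 children plus up to about 20 adolescents.
- Expected admissions: 50 × 0.001 = 0.05 to 50 × 0.015 = 0.75; with 70 enrolled, 0.07 to 1.05.
- Chance of at least one among 50: 1 − 0.999^50 = 4.9% to 1 − 0.985^50 = 53%.
- Expected shift: F(t) × k/n, at most 1.5 points.
- Realized shift with n = 50 and F = 80%: one admission gives 80% × 49/50 = 78.4%, three give 75.2%, five give 72.0%.
- If 5% were admitted (assumed), the simulated shift at Day 29 is about 4 to 5 points.

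**4. Assessment gaps.** Resolution on Day 12 is first recorded at Day 22, 22 − 12 = 10 days late, or 12 days late if that visit falls on Day 24 within its ±2-day window. Resolution on Day 23 is recorded 6 days late at Day 29. These delays make recorded recovery slower.

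**The case against.** **Faster recovery.** A reader might infer that both rules make recovery look faster throughout. The documents do not support that. A completer first clear at the last visit is dated Day 29, the latest date available, so the median does not move unless fewer than half have resolved by then. Only children who discontinue on a clear visit add earlier events, and the gaps after Day 11 work in the opposite direction.

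**Definition, not bias.** Collection stops at Day 29, so any definition lacks follow-up there, and the Protocol names sustained absence without defining it. With rare transient clear visits and a 7-day median, the present rule gave 94.0% against an assumed truth of 93.75%, closer than the confirmed 87.7%. This stands: most of the 6 to 12 points is a gap between definitions.

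**Hospitalized children.** One might infer that every hospitalized child should stay unresolved. That would over-correct for unrelated stays, which exclusion 32 permits at entry. One might also infer that a child already in hospital is censored at or before infusion. The hospitalization row of the schedule has no mark at screening or Day 1, and SAP 6.16.2.2 refers to admission after treatment, so post-dose admission is the natural reading, though 6.16.1.3 does not say so. Nor are admissions hidden: SAP 6.16.1.4, 6.16.2.1 and 6.16.2.4 report them.

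**Viral clearance.** The two-negative rule concerns a laboratory test. It shows that the SAP confirms elsewhere; it does not make the symptom definition inconsistent.

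**Importance.** The endpoint is exploratory in a single open-label arm, SAP 6.1 makes such analyses optional, and efficacy is extrapolated from adults. This limits the weight of the point. It does not change what the stated rules do.

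**Conclusion.** The point holds as a minor one. A single clear record at Day 29 or early discontinuation qualifies as sustained. Compared with a confirmation rule, this raises the Day 29 estimate by about 6 to 12 points. Within that gap, records that are truly false account for about 0.3 to 3.0 points among completers. Both ranges rest on assumed recovery medians of 7 to 12 days and transient-clear probabilities of 5% to 15%. Estimates to Day 22 barely change unless dropout is appreciable.

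Censoring at admission can only push the resolution curve upward compared with keeping those children unresolved. The expected size is at most about 1.5 points if the Protocol's background rate applies to this cohort, and a single admission among 50 would cost 1.6 points at 80% resolved. The daily description does not match the schedule and should be corrected, but its effect is to delay recorded recovery.

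**What to change.** In the SAP:

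- **6.16.1.3, sustained endpoint.** Require at least one later observed assessment with all symptoms absent; a carried-forward record should not count as confirmation. Without one, censor at the last assessment before the unconfirmed clear record. Keep the present definition as a sensitivity analysis and report how many events rest on one final visit.
- **6.16.1.3, hospitalization and death.** For a post-dose COVID-19-related hospitalization, or death, before resolution, use cumulative incidence with a competing event or keep the child unresolved to Day 29. Do not apply this to unrelated stays or to stays under way at enrolment.
- **6.3.6.** Align carry-forward and the death rule with these definitions and with the present/absent scale.
- **6.16.1.2.** Replace the daily description with Days 1 to 11, 22, 29 and ED. State that resolution dates after Day 11 are interval-censored, which delays recorded recovery.

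The cost is SAP wording and some programming, with no new data. The downside is that children first clear on Day 29 become censored, so the curve can gain no events after Day 22 and the Day 29 sustained proportion may be conservative. Showing the present definition beside it makes that visible.

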2.3. Section 3.0. Objective and Endpoints

Objectives	Endpoints
Primary	

 Characterize the pharmacokinetics of bebtelovimab after intravenous injection 	
 Area under the concentration-time curve (AUC) from 0 to infinity for bebtelovimab
Secondary	

 Safety description 	
 Safety assessments such as AEs and SAEs
Exploratory	

 Overall participant clinical status 	
 Proportion (percentage) of participants who experience the following events by Days 22, 29, 60 and 85 
 COVID-19 related hospitalization (defined as ≥ 24 hours of acute care) or death from any cause Proportion (percentage) of participants who experience the following events by Day 29 
 a COVID-19 related emergency room visit, or COVID-19 related hospitalization (defined as ≥ 24 hours of acute care), or death from any cause

 SARS-CoV-2 viral load reduction 	
 Change from baseline to 
 Day 5 Day 7 Day 11 SARS-CoV-2 viral load area under the response-time curve (AUC)

 Symptoms and resolution 	
 Time to absence of all symptoms Time to sustained absence of all symptoms Proportion of participants demonstrating absence of symptoms

 Characterize emergence of viral resistance to bebtelovimab 	
 Comparison from baseline to the last evaluable time point

 Safety 	
 Proportion (percentage) of participants who experience MIS-C

Abbreviations: AE = adverse event; MIS-C = multisystem inflammatory syndrome in children; SAE = serious adverse event; SARS-CoV-2 = severe acute respiratory syndrome coronavirus 2.

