### 6.3.6. Modified Last Observation Carried Forward

Analyses of symptom data, with the exception of change in symptom score, will utilize a modified last observation analysis (mLOCF). The mLOCF method is performed by carrying forward the last nonmissing postbaseline assessment to the subsequent missing assessments for analysis. For patients who die, all missing collection time points subsequent to the date of death will be imputed to Severe.

After mLOCF imputation, data from participants with nonmissing baseline and at least 1 postbaseline observation will be included in the analyses. The mLOCF imputation helps ensure that the maximum number of randomized participants who were assessed postbaseline will be included in the analyses and unfavorable terminal events are represented.

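### Sustained symptom resolution can rest on a single symptom-free report when that report is the child's last completed assessment

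*SAP*

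**What the plan says.** The protocol addendum (2.3, Objectives and Endpoints) lists two time-to-event symptom endpoints, one for absence of all symptoms and a separate one, "Time to sustained absence of all symptoms". It does not define 'sustained'.

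The SAP supplies the definitions:

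- **Resolution at one assessment (6.16.1.2):** "Symptom resolution is defined as all symptoms on the symptom questionnaire scored as absent". The recall period is 24 hours.
- **Sustained resolution (6.16.1.3):** "Sustained symptom resolution occurs at the first visit where symptom resolution is observed without reoccurrence at any subsequent visits".
- **Censoring (6.16.1.3):** "If a patient has not experienced symptom resolution by completion or early discontinuation of study/study treatment, the patient will be censored" at the last treatment-period visit. A further sentence reads: "If a patient is hospitalized, the patient will be censored at the date of hospitalization".
- **Sustained endpoint, derivation (6.16.1.3):** "Time to sustained symptom resolution in the same manner as described for initial symptom resolution". It has no censoring rule of its own.
- **Missing symptom data (6.3.6):** handled by "carrying forward the last nonmissing postbaseline assessment to the subsequent missing assessments for analysis".
- **Who completes the questionnaire (6.16.1.2):** "This questionnaire is for outpatient participants only".

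The Schedule of Activities (protocol addendum 2.2.1) marks COVID-19 symptoms at screening, Days 1 to 11, Day 22, Day 29 and ED. It marks none at Day 60 or Day 85.

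**The concern.** The protocol lists sustained absence separately from absence, so it should mean more than one symptom-free report. The SAP rule adds a requirement only when a later visit exists at which symptoms could return. With no later visit, nothing is tested and the child is still an event, because last-visit censoring applies only to children who have not resolved.

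At stake is the meaning of the label. A reader of the results will take 'sustained' to mean confirmed. In a single open-label arm there is no comparator in which the same misclassification would appear. Elsewhere the same SAP does ask for confirmation: viral clearance needs two consecutive negative tests (6.10), and a missing result is imputed as cleared only after two earlier negatives (6.3.2). The symptom endpoint has no counterpart.

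**Working it through.** The documents state no figure for this endpoint, so there is none to reproduce. The check has two parts.

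**1. The rule applied to constructed records.** The scheduled post-dose symptom days are 2 to 11, 22 and 29, which is 12 assessments. The literal rule takes the first clear visit with every later recorded visit also clear. The comparison rule also requires at least two consecutive clear reports.

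| Record | Literal rule | Two reports required |
|---|---|---|
| Clear only at Day 29 | Sustained, Day 29 | No event |
| Clear only at Day 4, then lost | Sustained, Day 4 | No event |
| Same child, later visits filled by mLOCF | Sustained, Day 4 | Sustained, Day 4 |
| Clear at Day 4, relapse, clear from Day 8, full follow-up | Sustained, Day 8 | Sustained, Day 8 |

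The first two rows show the gap. The third shows that a confirmation rule fails if filled values may serve as confirmation. The fourth shows that a confirmed resolution keeps its date under either rule.

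**2. Illustrative size.** Assume every child starts symptomatic, with daily recovery probability r and daily relapse probability q. None of these rates is in the documents. Put p = r/(r+q) and k = 1−r−q. Day 22 is 21 daily steps from the start and Day 29 is 28. With no dropout:

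- P(clear at Day 22) = p(1−k^21) and P(clear at Day 29) = p(1−k^28).
- P(clear at Day 29, given clear at Day 22) = p+(1−p)k^7.
- The literal rule counts P(clear at Day 29). The two-report rule counts P(clear at both). The difference is the share of children whose label rests on the last report alone.

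Worked for r = 0.15, q = 0.05: p = 0.75 and k = 0.80. P(clear at Day 22) = 0.743, P(clear at Day 29) = 0.749, and the conditional probability is 0.75+0.25×0.2097 = 0.802. Clear at both is 0.743×0.802 = 0.596. The difference is 0.749−0.596 = 0.152 to rounding, and 50×0.152 = 7.6 children.

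| r | q | Literal | Two reports | Per 50 children |
|---|---|---|---|---|
| 0.15 | 0 | 0.989 | 0.967 | 1.1 |
| 0.15 | 0.05 | 0.749 | 0.596 | 7.6 |
| 0.25 | 0.10 | 0.714 | 0.520 | 9.7 |
| 0.15 | 0.15 | 0.500 | 0.270 | 11.5 |

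The first row can be checked directly. A child is first clear between Days 23 and 29 with probability 0.85^21×(1−0.85^7) = 0.0329×0.679 = 0.0224, and 50×0.0224 = 1.1.

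A simulation of the three relapse settings (50,000 records each) with dropout of 0, 5, 10 and 20% gave 7.2 to 11.4 children per 50. The literal rule called 48-75% sustained, against 27-60% with two observed reports. Between 20% and 46% of sustained events rested on a single last report. ED visits and hospitalization were not modelled.

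The relapse settings imply that 26% (1−0.743) to 50% (1−0.500) of children are still symptomatic at Day 22. A reader who thinks that too many should expect a figure nearer the first row.

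**The case against.** The strongest opposing case is that little depends on this endpoint. It is exploratory, uncontrolled and untested, efficacy is extrapolated from adults, and SAP 6.1 makes exploratory analyses conditional on the team finding them warranted. Most children who clear before Day 11 and stay in follow-up will have several later reports. All of this stands and limits the weight of the point.

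Several stronger readings are tempting, and the documents do not support them.

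- **A child admitted after a clear report is certainly counted as sustained.** The hospitalization sentence in 6.16.1.3 carries no condition about prior resolution. It can be read as censoring that child at admission, or as irrelevant once an event has occurred. A discharged child also returns to outpatient assessment at any remaining visits. The text is ambiguous here.
- **Every child who discontinues after a clear report is misclassified.** The ED visit collects symptoms, so a child who attends it gives one more observed report. Exposure is confined to children lost without that visit and to those whose ED report is their first clear one.
- **Absence is carried forward past death.** SAP 6.3.6 imputes assessments after death to the severe category.
- **The endpoint is biased only toward recovery.** The last-report route is. However, one later recurrence of any item postpones the event, and mLOCF also carries forward the presence of symptoms.
- **Nothing else guards against a chance clear day.** SAP 6.16.1.2 also reports the proportions resolved at Days 5, 7, 11 and 22, and the data are listed.
- **The effect can be sized from children who never recover.** If such a child reports all clear with probability a at each independent assessment, the literal rule gives a and confirmation gives a². That returns the assumed input and does not show how many enrolled children are like this.

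**Conclusion.** The wording gap is real and does not depend on any simulation. SAP 6.16.1.3 requires no confirming assessment, no symptom assessment is scheduled after Day 29 or ED, and no other section of the SAP or addendum supplies a confirmation rule. A single symptom-free report at the last completed assessment therefore earns the sustained label.

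The size is uncertain: about 1 child in 50 with 15% daily recovery and neither relapse nor dropout, and about 7 to 11 in 50 under the assumed relapse and dropout rates. In the no-relapse case these children have truly recovered, so the label is unconfirmed but not false. The point is minor to moderate. It affects how one descriptive exploratory result is read, and leaves the primary pharmacokinetic analysis and the safety analysis untouched.

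**What to change.** Revise SAP 6.16.1.3 along these lines:

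1. Sustained resolution is dated at the first visit with all symptoms absent that is followed by at least one further observed assessment, with all symptoms absent at every later observed assessment.
2. Values filled by mLOCF do not count as observed for this purpose.
3. A child whose only clear report is the last completed assessment is censored at that assessment.
4. Reconcile the hospitalization sentence with the sustained definition. State whether a child admitted with COVID-19 after a first clear report is censored or counted as a reoccurrence, given that the questionnaire covers outpatients only.

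This needs no new data and no change to the visit schedule. Its main cost is that Day 29 can no longer be an event day: some children who truly recover between Day 22 and Day 29 will be censored, and the sustained proportion will be slightly lower. The confirming gap is also uneven, at one day between Days 10 and 11 but seven between Days 22 and 29, and a child clear on Days 4 and 5 and then lost would still count. If the team wants a firmer standard, a stated minimum symptom-free interval would provide it, with more censoring.
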